9.2.6.2 Routine SMBG monitoring

In addition to performing fasting SMBG every morning before breakfast, subjects or parents will perform SMBG monitoring 120-150 minutes post-dose at each meal. AFREZZA® doses will be adjusted based on these measurements ([Table2](#)).

9.2.6.3 7-point SMBG profiles

Once during the screening period in the week prior to the PK visit (Visit 2) and once per week during the treatment period 7-point glucose data (pre-meal and 120-150 minutes post-dose at breakfast, lunch, and dinner as well as at bedtime) will be obtained via SMBG readings. These data will be reviewed by the site and may be used to prescribe a regular supplemental post-meal AFREZZA® dose as per Section [8.1.5](#).

On these days, the starting and ending time for each meal will be reported in the e-Diary and in the e-CRF.

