8.3.3 Hypoglycemic Event

Definitions:

Hypoglycemic event:

The general symptoms of hypoglycemia most subjects experience include 1 or more of the following: headache, dizziness, general feeling of weakness, drowsiness, confusion, pallor, irritability, trembling, sweating, lightheadedness, shaky, increased appetite, rapid heartbeat and a

cold, clammy feeling. In severe cases, seizure, loss of consciousness, or even coma can occur.

All hypoglycemic events will be recorded on the Hypoglycemia eCRF page. In addition, severe hypoglycemia episodes and other hypoglycemia episodes which meet the criteria of SAE will also be records as SAEs in the AE page and safety complementary e-CRF.

Non-severe Hypoglycemic event

Non-severe hypoglycemic event is defined according to the ISPAD Clinical Practice Consensus Guidelines 2014 (3) as follows:

- SMBG levels <70 mg/dL and/or
- Symptoms of hypoglycemia that are relieved by the administration of carbohydrates

Severe Hypoglycemic event

Severe hypoglycemic event in children is defined according to the ISPAD Clinical Practice Consensus Guidelines 2014 (3) as an event associated with a seizure, coma, or loss of consciousness and will be considered an SAE.

Asymptomatic Hypoglycemic event

Asymptomatic hypoglycemic event is defined as an episode not accompanied by typical symptoms of hypoglycemia, but with a measured plasma glucose concentration < 70 mg/dL

Symptomatic hypoglycemic event

Symptomatic hypoglycemic event is defined as an episode accompanied with typical symptoms of hypoglycemia, with or without measured plasma glucose concentration, which is relieved by the administration of carbohydrates

Nocturnal hypoglycemic event

Nocturnal hypoglycemic event is defined as a hypoglycemia episode which occurs overnight during sleep.

Documented hypoglycemic event

Documented hypoglycemic event is defined as an episode with measured plasma glucose concentration <70 mg/dL. If such an episode is also accompanied by typical hypoglycemic symptoms, then it is defined as a symptomatic documented hypoglycemic event; otherwise, it is defined as an asymptomatic documented hypoglycemic event.

Table Presentation

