The last interval in each study period, i.e., Week 4 for the titration period and Month 12 for the extension period, will extend to the treatment end date of the study period, for subjects whose treatment duration is longer than 4 weeks or 12 months, for the two study periods respectively.

To derive event rate, observation time (in months) for a time interval will be calculated as

The number of days in the time interval which are between first dose date and last dose date (both inclusive)/30.4375.

Observation time will first be calculated for each individual subject, and then summed across all applicable subjects in the safety population.

- Time profile of hypoglycemic events in relation to pre-meal dosing

For each week in the titration period and each month in the extension period, event rate of hypoglycemia (in subject-month) will be calculated at 1 hour interval (i.e., [0,1] h, (1,2) h, (2, 3) h, and (3, 4h)) relative to the pre-meal insulin dosing time. A bar plot will be created with hypoglycemic events occurred following each pre-meal dose presented as a separate bar. Only hypoglycemic events occurred within 4 hours following a pre-meal dose will be included in this analysis.

To derive event rate, observation time for an hour (e.g., 0-1 h after breakfast) in a time interval (e.g., Week 1 in titration period) will be calculated as

The number of days in the time interval which are between first dose date and last dose date (both inclusive) /30.4375.

Observation time will first be calculated for each individual subject, and then summed across all applicable subjects in the safety population.

Subject Listings

For all hypoglycemic events and all severe events, detailed information of every event will be listed, by (in the order of) cohort, investigator site and subject.

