8.4.5 Fasting pre-breakfast SMBG and post-prandial SMBG

Schedule and Parameters

Fasting pre-breakfast SMBG and post-prandial SMBG at each meal will be measured daily throughout the study.

Table presentation

For each of the four parameters (fasting pre-breakfast SMBG and post-prandial SMBG at breakfast, lunch and dinner), average will be calculated at weekly intervals for the titration period and at monthly intervals for the extension period for each subject, and summarized by cohort. Same as for total daily dose and prandial dose, only data collected in the 2nd half of each interval (i.e., within 3 days prior to the each clinic visit in the titration period and within 2 weeks prior to each visit in the extension period) will be included in the analysis.

Baseline is defined as the average of all values collected prior to Visit 2. Change from baseline for a post-baseline time interval will be calculated as average of SMBG in the post-baseline time interval – baseline for each subject, and then summarized by cohort.

Graphical Presentation

For each of the four parameters, a Mean (SE) plot will be provided, presenting weekly average in the titration period and monthly average in the extension period (along with standard error) by cohort.

8.4.6 7-point SMBG

Schedule and Parameters

7-point SMBG (pre-meal and 120-150 minutes post-dose at breakfast, lunch and dinner as well as at bedtime) will be collected at screening visit, visits 6, 9, 12, 15 in the titration period, and visits 19, 22, 25, 28 in the extension period.

Table presentation

For each of the 7 parameters (pre-meal and 120-150 minutes post-dose 7-point SMBG at breakfast, lunch and dinner as well as at bedtime), average will be calculated at weekly intervals for the titration period and at monthly intervals for the extension period for each subject, and summarized by cohort. For each of these intervals, all data collected from the date of the previous on-site visit (including) to 1 day before the current visit for each visit are included in the summary.

Baseline is defined as the average of all values collected prior to Visit 2. Change from baseline for a post-baseline time interval will be calculated as average of 7-point SMBG in the post-baseline time interval – baseline for each subject, and then summarized by cohort.

Subject Listings

Detailed information of every measurement will be listed, by (in the order of) cohort, investigator site, subject and visit.

Graphical Presentation

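### On routine days the 120-150 minute glucose test falls in the 2-3 h bar of the hypoglycaemia time profile, so the pooled figure inflates that bar by ascertainment and can misplace the apparent time of risk

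*SAP*

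**What the plan says.** **The figure.** SAP 8.3.3 plans a time profile of hypoglycaemia in relation to pre-meal dosing, by week in the titration period and by month in the extension: "event rate of hypoglycemia (in subject-month) will be calculated at 1 hour interval". The four bars of each panel are printed in the SAP as follows: "i.e., [0,1] h, (1,2) h, (2, 3) h, and (3, 4h)) relative to the pre-meal insulin dosing time". On inclusion it says: "Only hypoglycemic events occurred within 4 hours following a pre-meal dose will be included in this analysis". The text does not split events by type for this figure. The observation time for each hour is defined as for the day profile, "The number of days in the time interval which are between first dose date and last dose date (both inclusive)/30.4375", so all four bars of a panel share one denominator.

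**The events.** The same section states: "Asymptomatic hypoglycemic event is defined as an episode not accompanied by typical symptoms of hypoglycemia". It also requires a measured glucose below 70 mg/dL. Protocol 9.2.6.4 has both asymptomatic and symptomatic episodes recorded, and asks subjects to test when they feel symptoms.

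**The testing.** Protocol 9.2.6.2: "subjects or parents will perform SMBG monitoring 120-150 minutes post-dose at each meal". SAP 8.4.5 confirms the frequency: "Fasting pre-breakfast SMBG and post-prandial SMBG at each meal will be measured daily throughout the study". Protocol 9.2.6.3 adds a profile once a week: "7-point glucose data (pre-meal and 120-150 minutes post-dose at breakfast, lunch, and dinner as well as at bedtime) will be obtained via SMBG readings". SAP Table 3 schedules Day 1 glucose samples after the breakfast dose out to 240 minutes. Protocol 9.2.5 allows ad hoc readings and does not state how many.

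**The concern.** The bars are meant to be compared with each other, but the chance of detecting a low is not the same in each. A symptomatic low can be noticed in any hour. An asymptomatic low is found only if a test coincides with it, and on an ordinary day the only routine test within four hours of a meal dose is at 2 to 2.5 h. A denominator of days does not correct for this. A tall 2-3 h bar could then reflect when children are tested, and short early bars could reflect the absence of tests.

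The protocol states that safety has not been evaluated in children (section 4.4) and that the data will inform dosing for Part 2 (section 4.2). Among the hypoglycaemia outputs this is the one arranged by time since dose, so readers will look to it for timing.

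**Working it through.** The plan gives no figure to reproduce here. The check maps the testing schedule onto the bars and then sizes the effect.

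**1. Window against bars.** 120-150 minutes is 2.0-2.5 h. Of the 31 whole minutes 120 to 150, 30 lie strictly between 2 and 3 h. The remaining one, exactly 120, lies in no bar, because the printed intervals are open at 2 h. They are also open at 3 h. Day 1 samples are scheduled at both 120 and 180 minutes.

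**2. Scheduled tests within 4 h of a pre-meal dose, Days 1-28.** Inputs:
- Routine tests: 27 days × 3 meals + 2 (Day 1 lunch and dinner) = 83, all placed in the 2-3 h bar.
- Day 1 breakfast (SAP Table 3): 30, 60, 90, 120, 180 and 240 minutes. With right-closed bars this is 2 / 2 / 1 / 1.
- Weekly profiles: 4 profiles × 3 extra readings (pre-lunch, pre-dinner, bedtime) = 12, which may or may not fall within 4 h of the preceding dose.

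| Extra profile readings | 0-1 h | 1-2 h | 2-3 h | 3-4 h | Total | Share in 2-3 h |
|---|---|---|---|---|---|---|
| none within 4 h | 2 | 2 | 84 | 1 | 89 | 94.4% |
| all 12 at 3-4 h | 2 | 2 | 84 | 13 | 101 | 83.2% |

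If the 12 readings fell in any other bar outside 2-3 h, the share would still be 84/101 = 83.2%. Ad hoc tests are not counted, because their number is not given.

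**3. Size with flat true risk.** Let lows start at a constant rate. Let s be the share that is symptomatic (recorded in any hour) and d the duration of a low in hours. An asymptomatic low is recorded only if it is in progress at the routine test. Each bar then holds s, and the 2-3 h bar holds s + (1 − s)d, so

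ratio of the 2-3 h bar to any other = 1 + (1 − s)d/s.

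| s | d (h) | Ratio |
|---|---|---|
| 0.75 | 0.25 | 1 + 0.25 × 0.25/0.75 = 1.08 |
| 0.50 | 0.50 | 1 + 0.50 × 0.50/0.50 = 1.5 |
| 0.30 | 0.75 | 1 + 0.70 × 0.75/0.30 = 2.75 |
| 0.25 | 1.00 | 1 + 0.75 × 1.00/0.25 = 4 |
| 0.20 | 1.00 | 1 + 0.80 × 1.00/0.20 = 5 |

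A simulation of 2,000,000 lows per scenario, with the test uniform on 120-150 minutes, agrees where the two overlap: 1.08, 1.50 and 3.98 for rows 1, 2 and 4. With all events symptomatic the four bars are equal at 25%. Values of s and d are assumptions; neither is in the documents.

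**4. Can the peak move?** Suppose true risk peaks in hour 1-2, with weights 1 : 2 : 1 : 0.5 (again an assumption). Simulated shares of the 1-2 h and 2-3 h bars:

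| Symptomatic share | 15-min lows | 30-min lows | 60-min lows |
|---|---|---|---|
| 10% | 27% / 52% | 18% / 69% | 10% / 83% |
| 25% | 37% / 36% | 30% / 48% | 21% / 64% |
| 50% | 42% / 27% | 38% / 33% | 32% / 44% |
| 75% | 44% / 24% | 42% / 26% | 39% / 31% |

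Hand check for 25% and 30 minutes. The test catches onsets in the preceding half hour, on average 15 minutes at weight 1 and 15 minutes at weight 2: 0.25 × 1 + 0.25 × 2 = 0.75. The 1-2 h bar is 2 × 0.25 = 0.50 and the 2-3 h bar is 0.25 + 0.75 × 0.75 = 0.8125. The total over four bars is 0.25 + 0.50 + 0.8125 + 0.125 = 1.6875, giving 30% and 48%.

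The plotted peak moves to 2-3 h at 10% symptomatic for every duration, at 25% for 30- or 60-minute lows, and at 50% only for 60-minute lows. At 75% it stays at 1-2 h.

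**The case against.** The case for leaving the figure alone has real weight.

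- **Other tests exist.** A reader might infer that 120-150 minutes is the only scheduled post-dose test and lies wholly in one bar. Day 1 and the weekly profiles schedule others, and exactly 120 minutes is unassigned. This stands, but those tests are at most about 17% of the scheduled total.
- **The shift is conditional.** A reader might infer that the figure does misplace the time of risk. Symptomatic and severe events are also plotted, timed by symptoms, and if they dominate the peak does not move. Ad hoc tests would soften the effect further. This stands: the documents support *can misplace*, not *does*.
- **Early hours are observed elsewhere.** SAP 8.2 plans glucose by nominal time at the PK visit (Table 14.2.3.1, Figures 14.2.3.1 and 14.2.3.2), on a fixed schedule. It would be wrong to say that nothing else informs early timing, although those outputs cover one dose.
- **Drug action.** The peak at about 12-15 minutes and near-baseline level at about 180 minutes (Protocol 4.1) are adult serum insulin concentrations. They do not establish that the untested hours carry the greatest glucose-lowering effect.
- **Low stakes.** Analyses are descriptive (SAP 8.1), and Appendix 3 does not mark Figure 14.3.1.2 for the DMC package. This limits the importance of the point.
- **Unseen shells.** Figure shells are in separate files (SAP Appendix 4) and might carry a split. The SAP text does not ask for one.

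**Conclusion.** The point holds in a limited form. On ordinary days the routine post-dose test falls in the 2-3 h bar apart from its 120-minute end point, asymptomatic events need a measurement, and the denominator ignores testing. The direction of bias follows from the design: the 2-3 h bar is inflated whenever the routine test finds asymptomatic lows. The pooled figure cannot separate timing of risk from timing of testing.

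The size is uncertain. Under flat risk the ratio runs from about 1.1 to 5 for assumed symptomatic shares of 0.2-0.75 and durations of 0.25-1 h, with no ad hoc tests. Whether the apparent peak moves depends on the same unknowns. This is a cheap improvement to a descriptive display, not a defect in a decision rule.

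**What to change.** In SAP 8.3.3 and the shell for Figure 14.3.1.2:

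1. Draw the time profile for symptomatic plus severe events as the main panel. SAP 8.3.3 already tabulates these categories separately, so the split only has to be carried into the figure.
2. Show asymptomatic documented events in a second panel, with the number of scheduled readings per bar and a footnote that their timing follows the testing schedule.
3. Do not plot a share of readings below 70 mg/dL in hours without routine scheduled readings. Ordinary-day readings in hours 0-2 are mostly ad hoc or prompted by symptoms, so that share would exchange one testing bias for another.
4. Show or flag Day 1 (the PK visit) apart from the rest of Week 1, because its sampling is different.
5. State bar ends so that every time falls in exactly one bar, for example [0,1], (1,2], (2,3], (3,4]. Since that choice sends exactly 120 minutes to the 1-2 h bar, either assign scheduled-window readings at 120 minutes to the 2-3 h bar or footnote them.

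The cost is SAP wording, one shell and a small derivation linking each reading to the preceding dose. No new data collection is needed. The downside is fewer events per panel.

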8.3.4 Cough

Cough will be reported as an adverse event on the AE page.

Graphical Presentation

- Day profile of cough

This figure will be created in the same way as the 'Day profile of hypoglycemic events' figure. Event rate of cough (in subject-month) will be calculated at 1 week interval during the titration period and at 1 month interval for the extension period. Only cough occurred between the first dose date and the last dose date will be included in this analysis

Subject Listings

All cough events will be listed, by (in the order of) cohort, investigator site and subject, and start date.

8.3.5 Pulmonary Function Testing

Schedule and parameters

Spirometry tests will be performed at screening, visits 2, 9, 15, and 16 in the titration period, visits 19, 22, 25, 28, and 29 in the extension period, as well as at the early termination visits in both periods. At each visit, Forced Expiratory Volume in 1 second (FEV₁) will be collected. At Visit 2, FEV₁ will be collected at several time points: -25 min, 18 min, 55 min, 125 min and 245 min relative to the time of first dose.

Table presentation

FEV₁ value and change from baseline will be summarized descriptively by cohort and analysis visit/nominal time point. For each post-baseline visit/time point, number and percentage of subjects with verified clinically relevant decline in pulmonary function from baseline (as indicated on the eCRF) will be presented by cohort. For percentage calculations, the total number of subjects in each cohort who attend the visit will be used as denominators.

Verified clinically relevant decline in pulmonary function will be captured as AE. A continuous decline will be captured as a single AE. The start date of this event is defined as the date when the criterion of clinically relevant decline (i.e., >15% decrease from baseline) is met for the first time, and the end date of this event is defined as the date when the criterion is no longer met. Each event will be assigned to a study period based on the start date. Duration (in days) of an event will be calculated as end date – start date + 1, and summarized by cohort and study period.

Subject Listings

For spirometry tests, detailed information of every measurement will be listed, by (in the order of) cohort, investigator site, subject and visit/time point.

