7.2 INCLUSION CRITERIA

Eligible subjects must meet all the following inclusion criteria for Part 1 of the study:

1. Written or oral assent from the pediatric subject and written informed consent from the parent(s) or legal guardian and a witness, as required by both state and federal laws and the local Institutional Review Board;
2. Children aged ≥ 4 and ≤ 17 years (enrolled into 3 age cohorts: 13 to 17, 8 to 12, and 4 to 7 years);
3. Clinical diagnosis of T1DM and using insulin for at least 1 year;
4. Currently receiving a regimen of basal/bolus insulin administered by MDI for at least 6 weeks prior to enrollment.
5. Subjects with pre-breakfast SMBG values between 80 and 250 mg/dL for 5 of 7 documented daily readings obtained in the week prior to Visit 2 (reading to be taken using glucometer provided at Screening Visit 1) and reported via the e-Diary;
6. Subjects on a regimen of insulin via continuous SC insulin infusion may be enrolled if they satisfy all other enrollment criteria and are willing to convert to MDI for the duration of the study, beginning 6 weeks prior to enrollment. They must continue to meet all enrollment criteria after converting to the MDI regimen;
7. Total daily insulin dose ≤ 1.5 units/kg/day with a minimum of 3 units of RAA at every meal.
8. HbA1c 7.0% to 10.0% at the time of screening;
9. Fasting serum C-peptide ≤ 0.3 ng/mL;
10. Forced expiratory volume in 1 second (FEV₁) $\geq 70\%$ of National Health and Nutrition Examination Survey (NHANES) III predicted for children ≥ 8 years of age or Wang predicted for children < 8 years of age (8), (9);
11. Forced vital capacity $\geq 70\%$ of NHANES III predicted for children ≥ 8 years of age or Wang predicted for children < 8 years of age (8), (9);
12. Subjects of childbearing potential must use “highly effective” methods of contraception. These include, for example, a state after surgical sterilization, hormonal intrauterine devices (coil), oral hormonal contraceptives, sexual abstinence or a surgically sterilized partner.

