3 STUDY DESIGN

3.1 Overview of Study Design

MKC-TI-155 Part 1 will be a single-arm, multi-center, open-label, uncontrolled study to evaluate PK, safety, and ability to titrate AFREZZA[®] in children ages 4 to 17 years with T1DM, who were previously on a regimen of basal-bolus insulin therapy administered by multiple daily injections (MDI).

The structure of the study is as follows:

- Single dose PK at breakfast
- 4-week titration period starting at lunch after PK evaluation
- Optional 52-week safety extension

The screening period is up to 3 weeks. On Day 1, eligible subjects will receive a single dose of AFREZZA[®] prior to PK sampling. There will be 3 different doses of AFREZZA[®] for the PK study. The AFREZZA[®] dose (4, 8, or 12 units) will be based on the dose of SC RAA that the subject would usually receive for a breakfast containing a predetermined level of carbohydrate, comprising approximately 50% of the total caloric content. After this starting dose, each subject will be titrated with AFREZZA[®] TI according to the titration rules given in the protocol (2).

After the 4-week titration period, subjects will have the option to continue in a 52-week extension study at the Investigator's discretion. For subjects who opt not to continue treatment with AFREZZA[®], a follow-up visit will occur approximately 1 week after the end of AFREZZA treatment for safety assessments (duration of 1 day). For subjects who participate in the extension study, an end-of-study follow-up visit will be conducted 4 weeks after the 52-week treatment period.

The study will be conducted sequentially in age groups beginning with Cohort 1. Approximately 46 subjects will be enrolled sequentially into 3 age cohorts:

- **Cohort 1: 13 to 17 years;** approximately 18 subjects distributed across 4, 8, and 12 unit starting dose groups. Before proceeding to Cohort 2, at least 14 subjects must be dosed (i.e., must complete Visit 2). Of those, at least 6 subjects must receive the 8 unit dose.
- **Cohort 2: 8 to 12 years;** approximately 14 subjects distributed across 4 and 8 unit starting dose groups (the sample size may be adapted after taking the PK data from Cohort 1 into

account). Before proceeding to Cohort 3, at least 6 subjects must have completed Visit 15, and all subjects in Cohort 2 must have been evaluated for PK.

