5.2 Baseline

Baseline values are defined as the last measurements collected on or prior to Study Day 1 before dosing, unless otherwise specified.

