5.4 Study Period

Two study periods are defined: an approximately 4-week titration period (Visit 2 – Visit 16, including PK assessments at Day 1) followed by an optional 52-week extension period (Visit 17 – Visit 29). Participants in the titration period are defined as subjects who take at least one dose of study drug in the titration period and participants in the extension period are defined as subjects who complete the titration period and opt to participate in the extension study.

Start date of the titration period is defined as Study Day 1. For subjects who do not participate in the extension period, end date of the titration period is defined as the last visit/contact date; for

subjects who participate in the extension period, end date of the titration period is defined as the date of Visit 15.

Start and end date of the extension period are defined for subjects who participate in the extension period only. Start date is defined as date of Visit 15 +1 day, and end date is defined as the last visit/contact date.

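### In the SAP's 52-week extension, FEV1 change and the >15% decline flag are not adjusted for growth, so moderate losses of lung function can be masked

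*SAP*

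**What the plan says.** **Measure and flag.** SAP 8.3.5 states that FEV1 "value and change from baseline will be summarized descriptively by cohort and analysis visit/nominal time point". It names no unit, percent predicted, z-score or other adjustment for age or height. The same section dates a decline event from when the "criterion of clinically relevant decline (i.e., >15% decrease from baseline) is met for the first time" and closes it once the criterion stops being met. The by-visit count uses the site-verified eCRF entry.

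**Baseline and follow-up.** SAP 5.2: "Baseline values are defined as the last measurements collected on or prior to Study Day 1 before dosing". Nothing resets this for the extension. SAP 3.1 lists an "Optional 52-week safety extension". For that period SAP 5.4 says "Start date is defined as date of Visit 15 +1 day", and SAP 8.1.1.2 (Table 2) sets FEV1 windows at Months 3, 6, 9 and 12 and at follow-up.

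**What could correct for growth.** SAP 8.3.7 takes height at screening only, and SAP 3.1 describes a single-arm, uncontrolled study. Protocol 7.2 (criteria 10 and 11) already uses percent predicted for eligibility, with one reference equation from age 8 and another below age 8.

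**Versions.** The supplied protocol is Amendment 3. Its sections 6.1 and 6.3 end with titration and a follow-up visit; the only trace of an extension is a Flow Chart 1.1 footnote on test strips. SAP section 10 cites Amendment 2.

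**The concern.** FEV1 can be expected to rise with growth in children aged 4 to 17. If it does, a child's value at Month 12 should lie above the pre-dose baseline, and a child who merely stays level has lost ground. With a fixed baseline, no updated height and no comparator, the planned outputs cannot separate growth from loss. The error runs in one direction, toward no harm, and increases with follow-up.

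A clinically relevant decline in pulmonary function is one of the four adverse events of special interest. Protocol 4.4 reports that adults had a 40 mL greater FEV1 decline than comparators, seen within the first 3 months and persisting. The titration period lasts 4 weeks, so the extension is where this study would be more likely to see a change of that kind. The planned summary of event duration is exposed too: an event can close because the child has grown, not because lung function has recovered.

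**Working it through.** The plan gives no calculation for the 15% threshold, so there is no stated figure to reproduce. The check asks what loss against expected FEV1 the flag detects.

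**Inputs**
- Threshold: 0.85 of baseline (SAP 8.3.5).
- Time since Day 1: Visit 15 is Day 29, so the extension starts on Day 30. The Month 12 target is Day 30 + 365 = Day 395, which is 394 days after Day 1. In the same way Months 3, 6 and 9 fall 120, 212 and 303 days after Day 1, and Week 4 falls 28 days after. Years *t* = days / 365.25.
- Growth *g* per year: **not in the documents**. Assumed range 0 to 15%.

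**Formulas**
- Expected FEV1 = baseline × (1+g)^t.
- Loss against expected at which the flag trips = 1 − 0.85/(1+g)^t.
- Observed change from baseline for a true deficit *d* = (1+g)^t × (1−d) − 1.

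Example: g = 5% at Month 12 gives t = 394/365.25 = 1.079 and 1.05^1.079 = 1.054, so the trip point is 1 − 0.85/1.054 = 19.4%.

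**Loss against expected needed to trip the flag (%)**

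| Visit | g = 0% | 3% | 5% | 10% | 15% |
|---|---|---|---|---|---|
| Week 4 | 15.0 | 15.2 | 15.3 | 15.6 | 15.9 |
| Month 3 | 15.0 | 15.8 | 16.4 | 17.6 | 18.8 |
| Month 6 | 15.0 | 16.4 | 17.4 | 19.6 | 21.6 |
| Month 9 | 15.0 | 17.1 | 18.4 | 21.5 | 24.3 |
| Month 12 | 15.0 | 17.7 | 19.4 | 23.3 | 26.9 |

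**Observed change at Month 12 for a given true deficit (%)**

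| True deficit | g = 3% | 5% | 10% | 15% |
|---|---|---|---|---|
| 10% | -7.1 | -5.1 | -0.3 | +4.6 |
| 20% | -17.4 | -15.7 | -11.3 | -7.0 |
| 25% | -22.6 | -20.9 | -16.9 | -12.8 |

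A 20% deficit is flagged at 3 to 5% growth and missed at 10 to 15%. A 25% deficit is flagged up to 10% growth and missed at 15%.

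**Event duration.** At g = 5%, a child with a constant 18% deficit shows -16.7% at Month 3, -15.6% at Month 6 and -14.6% at Month 9. The event would close by Month 9 through growth alone.

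**Absolute scale.** For an assumed baseline of 1.0 to 3.5 L, growth by Month 12 adds 32 to 113 mL at 3% a year and 54 to 189 mL at 5%. That is of the same order as the 40 mL adult difference, or larger.

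**The case against.** Several points on the other side stand.

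- **Unit.** A reader might infer that FEV1 will be analysed in raw litres. The documents do not say so: SAP 8.3.5 and the title of Table 14.3.4.1 give no unit, and the table shells are separate files. What is documented is that no growth adjustment is specified. Even a tabulated percent predicted would rest on screening height.
- **Extent of masking.** A reader might infer that growth hides real loss in general. It hides moderate losses late in the extension. The Day 1 readings come within hours of baseline, the Week 4 trip point moves by less than one percentage point, and large losses are still caught.
- **Growth rate.** It is assumed, not documented. At zero growth there is no masking, and the oldest cohort, which is also the largest (18 of 46), may include children who grow little.
- **Extension status.** The whole effect sits in an extension that the Amendment 3 design does not contain. This makes the point conditional. It does not remove it, because the SAP still specifies extension windows, event periods and summaries.
- **Importance.** A reader might call this a main safety question. Protocol 4.4 lists FEV1 decline as an additional consideration, outside its important identified and potential risks. A 15% individual flag is not built to find a 40 mL mean difference, and percent predicted without a comparator would not isolate one either.
- **Site verification and listings.** Sites verify declines, and every spirometry reading is listed. Neither supplies a growth-adjusted criterion.
- **Risks in a fix.** The reference equation changes at age 8, and a 7-year-old can turn 8 during 52 weeks. Redefining the decline in the SAP alone would separate the analysed event from the one that sites report.

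**Conclusion.** As written, the SAP's extension FEV1 change is biased upward, and its decline flag loses sensitivity, in any child whose FEV1 grows. At Month 12 the flag needs a loss against expected of about 15, 17.7, 19.4 or 23.3% for assumed growth of 0, 3, 5 or 10% a year. Over the 4-week titration period the effect is negligible.

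A reader might go on to conclude that the special-interest event will be under-counted. That depends on growth and on losses that nobody yet knows, so it is a risk and not an established result. The finding rests on three things: the extension is analysed as the SAP describes, FEV1 grows by some positive amount, and no growth adjustment is made in the unseen shells. Confidence is moderate.

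**What to change.** 1. **Reconcile the documents.** The SAP includes the extension and cites Amendment 2; protocol Amendment 3 has no extension in its design. State which applies and whether extension data will be analysed.
2. If they will be:
   - State the FEV1 unit.
   - Add FEV1 percent predicted, value and change from baseline, at extension visits, using the eligibility reference equations. Keep one equation per child so that turning 8 does not create a step. By its title in the protocol bibliography, the source for the under-8 equation covers ages 6 to 18. A child can therefore stay on it past 8, but the SAP should say how it is applied at ages 4 and 5.
   - Report a supplementary analysis flag for a fall of more than 15% in percent predicted, relative to the child's own baseline, beside the existing criterion. For example, a child starting at 80% predicted would be flagged below 0.85 × 80 = 68%. Leave the site-reported adverse event definition unchanged.
   - Record height at the extension spirometry visits (19, 22, 25, 28, 29 and early termination), where weight is already taken.
3. **Where heights were not taken,** state in the report that stable unadjusted FEV1 cannot be read as no loss of lung function.

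If expected growth follows the reference equations, the supplementary flag trips at a 15% deficit at every visit. This is a cheap improvement. Its downside is the height reading at those visits, which is a protocol change, and one more table block.
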